Topical antifungals are generally recommended for the treatment of distal and lateral subungual onychomycosis with less than 50% of the visible nail plate surface area without matrix involvement, < 2-mm nail plate thickness, and ≤ 4 nails involved (39,40). FDA-approved topical agents that have shown efficacy for antifungal use include ciclopirox nail lacquer, efinaconazole, and tavaborole. According to the package insert for ciclopirox 8% nail lacquer, a complete cure was observed in 5.5% and 8.5% of cases, and the mycologic cure was 29% and 36% (41). Efinaconazole 10% solution had 17.8% and 15.2% complete cure incidences and 55.2% and 53.4% incidences of mycological cure; and tavaborole displayed 6.5% and 9.1% incidences of complete cure rate and 31.1% and 35.9% incidences of mycological cure (41-43). Interestingly, confirmatory mycology testing before treatment in not cost effective with terbinafine whereas it is with efinaconazole (9). Topical therapy can be relatively expensive, with average monthly supply costs of \$76.43 for ciclopirox, \$687.54 for efinaconazole, and \$1885.75 for tavaborole (44-46).

The Tolcylen[™] antifungal solution consists of tolnaftate as an active ingredient and undecylenic acid, lactic acid, propylene glycol and urea as delivery system ingredients. The patented low surface tension Tolcylen[™] Solution is the first product of its kind to combine FDA-approved antifungal medication with nail renewal, cosmetic and penetration enhancing ingredients. Tolnaftate, a thiocarbamate antifungal, blocks ergosterol biosynthesis, thus inhibiting fungal membrane formation (47). Tolnaftate has been used for superficial mycotic infection, such as tinea pedis due to Trichophyton rubrum, Trichophyton mentagrophytes, and Epidermophyton floccosum (48, 49). The delivery system ingredients in Tolcylen[™] also have antifungal properties, and they convey a cosmetic effect in that they improve nail appearance. In a multicenter, randomized, double-blind, placebo-controlled trial, a statistically significantly greater incidence of mycological cure was observed with a topical preparation of urea, propylene glycol and lactic acid compared to placebo; specifically, 27.2% vs. 10.4% placebo for ≤ 50% nail involvement, and 19.1% vs 7.0% placebo for 51-75% nail involvement, after 26 weeks of treatment for distal and lateral

CONFIDENTIAL

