Table 1 Topical solution tube site-participant designation*

CONFIDENTIAL

A4	B4	C4	D4	E4	F4	G4	H4	J4
A5	B5	C5	D5	E5	F5	G5	H5	J5
A6	B6	C6	D6	E6	F6	G6	H6	J6
A7	B7	C7	D7	E7	F7	G7	H7	J7
A8	B8	C8	D8	E8	F8	G8	H8	J8
A9	B9	С9	D9	E9	F9	G9	H9	J9
A10	B10	C10	D10	E10	F10	G10	H10	J10
An	Bn	Cn	Dn	En	Fn	Gn	Hn	Jn

*This designation correlates with the randomization schedule and enables the principal investigator to keep track of active and placebo distribution and use.

A study coinvestigator, not participating at a study site, and not tasked with data analyses, will maintain the random allocation code, which will contain this same information as well as the randomly allocated topical solution, denoted as either the placebo nail solution or the active topical nail solution.

Inclusion and Exclusion Criteria

Inclusion criteria for participation in this study include:

- 1. Male or female participants aged 18 years or older;
- 2. If female is of childbearing potential, she must not be pregnant at the time of enrollment and she must be using an accepted form of birth control during the study treatment period (acceptable forms include: postmenopausal, surgical sterility, complete abstinence, sterilized sexual partner, tubal occlusion, copper-T intrauterine device, levonorgestrelreleasing intrauterine device, medroxyprogesterone injections, etonogestrel implants, combined pills, norelgestromin/ethinly estradiol transdermal system, intravaginal device, or Cerazette pill; and for males the use of a condom with spermicide or surgical sterility);
- 3. Participant has a diagnosis of onychomycosis diagnosed by means of history, physical examination, and positive (evidence of fungal hyphae) mycological tissue examination by periodic acid-Schiff (PAS) staining;
- 4. At least one toe nail with distal subungual involvement, localized to any toe, with at least 10% involvement and including up to 100% involvement of the visible nail plate, any nail plate thickness, with the index nail being the most involved per inspection by the on-site investigator and agreed upon by the designated co-investigator study doctor ([name], DPM), who will inspect specific clinical photographs of the involved nail/s (the photographs will be obtained at each study site using a specified method, as demonstrated to site investigators, so that the clinical features are appropriately demonstrated);

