A visible nail plate involvement score (Table 3, below) will be used to assess the clinical appearance of an involved toenail, at baseline and then repeated at each follow up visit. This score was designed to provide a continuous numeric value to rate the gross clinical appearance of dystrophic and/or mycotic toenails. The score ranges from a low of 7 to a maximum of 27, with a lower score indicative of a more normal appearing toenail and a higher score indicative of more advanced toenail dystrophy based on gross clinical inspection. This scoring scale was deemed reliable when tested for inter- and intra-rater reliability; wherein, 4 observers rated 40 nails on two separate occasions 3 weeks apart (Pearson's product-moment correlation coefficients for inter-rater reliability ranged from

CONFIDENTIAL

0.8849 to 0.9609 and the intra-rater reliability ranged from 0.8768 to 0.9687). Pearson's product-moment correlation coefficients range from -1 (100% negative association, or perfect inversion) to +1 (100% positive association, or perfect agreement), with a value of zero indicative of the absence of an association. In general, correlation coefficients with absolute values ranging from 0.60 to 1.00 are considered strong, and those <0.40 are considered weak. Our assessment of this scoring scale for visible toenail involvement indicated strong positive agreements for between and within rater correlations. The index toenail will be rated either by the blind site investigator, or submitted as a photograph for blind study coinvestigators to score. A decrease in the VNPIS of \geq 60% at any follow up visit will be considered a clinical cure.

	/	
Nail plate characteristics		Point/s
Type of apparent onychomycosis [select one]	White superficial	1
	Distal subungual	2
	Proximal subungual	3
	Any combination of above	4
Longitudinal segmental involvement of visible nail	≤ Distal half	2
plate (location of gross visible nail plate	> Distal half, excluding lunula	3
involvement) [select one]	Extending proximal to lunula	4
Apparent percentage involvement of visible nail	≤ 25%	2
plate [select one]	> 25% ≤ 50%	3
	> 50% ≤ 75%	4
	> 75%	5
Overt gross appearance of involved nail. For	Overtly thickened nail plate	2
thickness, inspect distal margin of visible nail plate	Lytic, overtly lifted from nail bed	3
and bed (including hyperkeratosis of nail bed	Onychauxis, gryphosis,	1
attached to plantar surface of nail plate) compared	clubbed, ram's horn shape	4

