to other toenails [select all that pertain]	Split, canaliformis, fragmented	5
	TOTAL SCORE (range 7 to 27)	

Table 3 Visible Nail Plate Involvement Score (VNPIS)

Study Visits and Procedures

Investigators participating in this clinical trial will undergo a thorough review of the protocol via teleconference prior to initiation of the investigation. Participating site personnel and the study sponsor, as well as the PI, have already engaged in teleconference in regard to preparation of the study materials and planned involvement. Study visits and procedures will proceed as follows:

- 1. Screening and Pre-treatment Evaluation
- 2. Initiation of Study Treatment
- 3. 3-Month Follow-up Visit
- 4. 7-Month Follow-up Visit
- 5. 9-Month Follow-up Visit

CONFIDENTIAL

When and How to Withdraw Participants

Participation in this research study is voluntary, and any participant can withdraw from the study at any time of their own choice. Although it is desired that all participants, once randomized into a treatment arm, remain in the study until completion of the follow-up visits, it may be necessary to discontinue a volunteer's participation if the participant fails to adhere to the protocol requirements, worsening of fungal infection to the involved toenail or if the participant withdraws his or her consent. Beyond the routine potential complications related to topical application of active topical nail solution, participation in this research project conveys no foreseeable safety hazards. If the volunteer desires, or if the study staff decides, to discontinue a volunteer's participation, it can be done on an immediate basis without the need for a tapered withdrawal period. Participants who choose not to continue with the study protocol until the end of the follow-up period, due to the development of a complication related to their participation in the study, or for any other reason, will be censored, and their last observed data carried forward in the statistical analyses.

Data Collection and Follow-up for Withdrawn Participants

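### On the stated VNPIS range of 7 to 27, a nail with a baseline score of 17 or less cannot meet the 60% clinical cure rule, and Table 3 gives no score for a clear nail

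*Protocol*

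**What the plan says.** The Protocol section on the VNPIS gives the range: "The score ranges from a low of 7 to a maximum of 27". It gives the direction as well: "with a lower score indicative of a more normal appearing toenail". The last row of Table 3 repeats the range: "TOTAL SCORE (range 7 to 27". The same section sets the response rule, a decrease in the VNPIS of at least "60% at any follow up visit will be considered a clinical cure". Nothing subtracts the floor, and no minimum baseline score is required.

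Table 3 has four items. The first is a forced single choice, "Type of apparent onychomycosis [select one", worth 1 to 4 points. Longitudinal extent (2 to 4) and percentage involved (2 to 5) are also single choices. Gross appearance is a tick-all item, "to other toenails [select all that pertain", with features worth 2, 3, 4 and 5. No item has a normal or none option.

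Inclusion criterion 4 admits a wide range of severity: "with at least 10% involvement and including up to 100% involvement of the visible nail plate, any nail plate thickness".

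Under Statistical Methods, the primary endpoint is presence or absence of hyphae on PAS stain. The secondary endpoint based on the VNPIS is change in the score. The Research Question section expects a higher incidence of both clinical and mycological improvement on active treatment.

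**The concern.** A percentage fall on a raw score has its usual meaning only if the best score is zero. Here the best stated score is 7, so the largest fall a nail can show depends on where it starts. A mild nail that improves as far as the scale allows is still recorded as not cured, while a severe nail can be recorded as cured with points to spare. Nails with low baselines are then built-in failures in both arms.

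Two things are at stake. First, the 60% rule is the only numerical definition of clinical response in the protocol, so it is the natural measure for the clinical half of the hypothesis. If a share *s* of participants cannot qualify, a true difference *D* among the rest shrinks to (1 − *s*)*D*. As an illustration only, a 20-point difference becomes 15, 10 or 5 points if *s* is 25%, 50% or 75%; the protocol gives no value for *s*. Second, the nails most affected are the less deformed ones, and the Review of the Literature says "Topical antifungals are generally recommended for the treatment of distal and lateral subungual onychomycosis with less than 50% of the visible nail plate" involved. The trial enrols well beyond that group but includes it.

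**Working it through.** **Inputs.** Item points, stated range and 60% threshold are from the VNPIS section and Table 3. Eligible severity is from inclusion criterion 4.

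**Reproducing the stated range.**
- Minimum with one gross feature ticked: 1 + 2 + 2 + 2 = 7.
- Maximum: 4 + 4 + 5 + (2 + 3 + 4 + 5) = 27.

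Both agree with the protocol. The low of 7 requires at least one gross feature to be ticked.

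**Cut-off.** Cure requires (B − F)/B ≥ 0.60, so F ≤ 0.40 × B, where B is baseline and F is follow-up. With F no lower than 7, B ≥ 7/0.40 = 17.5, so 18 on an integer scale.

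| Baseline | Largest possible fall (to 7) | Can qualify? |
|---|---|---|
| 8 | 1/8 = 12.5% | no |
| 12 | 5/12 = 41.7% | no |
| 16 | 9/16 = 56.2% | no |
| 17 | 10/17 = 58.8% | no |
| 18 | 11/18 = 61.1% | yes |
| 27 | 20/27 = 74.1% | yes |

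Scores 7 to 17 are 11 of the 21 possible values.

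**Scoring patterns below 18.** For a distal subungual nail the type item is 2. There are 3 longitudinal options, 4 percentage options and 15 non-empty sets of gross features: 3 × 4 × 15 = 180 patterns. A total below 18 means extent plus percentage plus gross points of at most 15.

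| Extent + percentage | Ways | Largest gross total allowed | Feature sets within it | Patterns |
|---|---|---|---|---|
| 4 | 1 | 11 | 13 | 13 |
| 5 | 2 | 10 | 12 | 24 |
| 6 | 3 | 9 | 11 | 33 |
| 7 | 3 | 8 | 9 | 27 |
| 8 | 2 | 7 | 8 | 16 |
| 9 | 1 | 6 | 6 | 6 |

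The sum is 119 of 180 (66%); 61 (34%) can qualify.

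Two cases make this concrete:
- A distal subungual nail with one gross feature scores at most 2 + 4 + 5 + 5 = 16, so it can never qualify.
- With up to 50% involvement not reaching the lunula, a nail with one or two gross features scores at most 2 + 3 + 3 + 9 = 17, so it cannot qualify either.

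**Sensitivity to the floor.** Table 3 does not say how a clear nail is scored, so the cut-off (floor/0.40) was recomputed for other floors.

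| Best attainable score | How it could arise | Lowest baseline that can qualify | Patterns that cannot (of 180) |
|---|---|---|---|
| 8 | type stays distal subungual, one feature ticked: 2+2+2+2 | 20 | 148 (82%) |
| 7 | the stated low: 1+2+2+2 | 18 | 119 (66%) |
| 6 | type stays distal subungual, no feature ticked: 2+2+2 | 15 | 66 (37%) |
| 5 | no feature ticked: 1+2+2 | 13 | 33 (18%) |
| 0 | clear nail scored as nothing | none | 0 |

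The last three rows contradict the stated low of 7.

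**The case against.** The strongest reply is that a score of 7 is not a normal nail. In Table 3 it describes white superficial disease in the distal half, up to 25% involved, with an overtly thickened plate. A reader might infer that a completely normal nail can never be called cured from a baseline below 18. The documents do not support that without qualification, because they never say what a normal nail scores. If gross appearance may be left blank, the cut-off falls; if a clear nail scores 0, the problem disappears. This objection stands. It makes the conclusion conditional on the range stated twice in the protocol, and it exposes the more basic defect that the table cannot score a clear nail.

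A reader might also infer that most participants are affected. That is not supported. The pattern counts weight every combination equally, no baseline VNPIS distribution is given, and the index nail is the most involved one, which pushes baselines up.

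Nor is the trial's main efficacy comparison diluted. The primary endpoint is PAS, the listed VNPIS endpoint is change in score, and Statistical Methods names no analysis of VNPIS-defined cure.

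Finally, one might infer that the 60% rule decides who may end application early. The Study Summary and the Study Duration section speak of clinical and mycological cure, and Duration of Administration speaks of clearance. None of them cites the VNPIS.

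What remains is that the protocol fixes a scale and a threshold that do not work together. That is a rule stated badly, not a detail left to an analysis plan.

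**Conclusion.** The point holds in a limited form. Taking the stated floor of 7 and a fall on the raw score, no baseline of 17 or less can be a clinical cure, even when the nail reaches the best score the scale offers. That covers 66% of the distal subungual patterns with at least one gross feature, and from 18% to 82% for floors of 5 to 8. Only a clear-nail score of 0, at odds with the stated range, brings it to none. The share of participants affected is unknown.

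The effect is confined to the clinical cure classification and to the clinical half of the hypothesis in so far as that classification is used for it. The PAS primary endpoint and the VNPIS change score are untouched. This should be fixed, but it does not threaten the primary analysis.

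**What to change.** Before scoring and unblinding:

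1. Add a none option to each Table 3 item, so that a clear nail has a defined score, and restate the range to match.
2. Define the 60% response as (baseline − follow-up)/(baseline − clear-nail score). A nail that clears then counts as 100% from any baseline. If none is worth 0 in every item, this is the same as the raw percentage fall.
3. Call that response clinical improvement, and keep clinical cure for a nail at the clear-nail score.
4. Reconcile the Study Summary, Study Duration, Duration of Administration and VNPIS sections on what clinical cure or clearance means. This review takes no position on when application should end.

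Subtracting 7 without the first step would not be enough. A distal subungual nail with one feature reaches no lower than 8 unless its type is rescored. One with no feature ticked scores 6, giving a negative denominator. A baseline of 8 would turn a one-point change into a 100% fall.

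The cost is a wording change to one table and a few sentences, with no new measurements. The drawbacks are that the stated range changes and that the quoted inter- and intra-rater reliability figures (4 observers, 40 nails) apply to the old scoring.

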The recruitment and screening period for potential participants will be 12 months (in order to identify 70 eligible participants) following the decision to initiate the protocol. It is expected that 70 participants will be informed and consented, and enrolled in the study, by approximately 12 months. Treatment for each participant will be carried out for a total of 9 months, or less if there is evidence of clinical

CONFIDENTIAL

and mycological cure prior to that time. The 9-month follow up visit will serve as the primary efficacy endpoint, in keeping with the usual expected minimum 7 to 9 -month duration of time expected for a full replacement of the visible nail plate in a typical adult human. Thereafter, a 3-month period will be allotted for completion of mycological testing and data collection. An additional 3 months will be allotted for completion of the analyses and 3 more months to write the report describing the study and submission of the manuscript for consideration for publication in a refereed journal. It is, therefore, estimated that the duration of time necessary for the completion of this protocol, data analysis, and preparation of the final report, will be approximately 35 months.

Study Centers

This study will be carried out at multiple clinical offices, under the guidance of different CITI-trained investigators, including:

- [name], DPM; Ankle & Foot Associates, [contact] (cell) Contact: Self; [contact], [name]. Site A
- [name], DPM; St Cloud Foot & Ankle; [contact] (cell) Contact: self; [contact] [name]. Site B
- [name], DPM; National Foot and Ankle, [contact] (cell) Contact: Self; [contact], [name]. Site C
- 4. [name], DPM; Family Foot Care, [contact] (cell) Contact: Self; [contact], [name]. Site D
- [name], DPM (the Principal Investigator); Foot & Ankle Specialists of Nevada, [contact] (cell) Contact: Self; [contact], [name]. Site E
- [name], DPM; A Step Ahead Foot and Ankle, [contact] (cell) Contact: Self; [contact], [name]. Site F
- [name], DPM, [name], DPM; The Division of Podiatry at The GW Medical Faculty Associates, [contact]) Contact: Office; [name]. Site G.

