It should be noted that the method of supply and application of both the placebo and the active topical nail solution is consistent with the standard method of use approved by the FDA monograph for use of an over-the-counter topical cosmetic agent, in accordance with the existing FDA monograph approved method for the treatment of dystrophic nails (see Tolcylen[™] label, Attachment 1). Participants in each group will be verbally instructed in the proper method of application of the topical solution and will also receive written instructions describing the study regimen and application technique (Attachment 2).

Upon arrival to the clinic for follow-up evaluation and care, the study participant will meet with a blinded investigator in the treatment room. The blinded investigator will review the study protocol and discuss any questions that the participant may have. The blinded investigator will inspect the participant's affected toes and procure the required information (clinical and photographic data) as delineated in this protocol.

Duration of Administration

For participants in both groups, maintenance of topical application of the assigned solution on the mycotic toenail/s will continue for a period of up to 9 (nine) months, for the purposes of the study. This duration of application is based

CONFIDENTIAL

on an average adult nail growth rate of 9 months for emergence from the proximal nail fold to the distal margin of the nail bed. Follow-up inspections will take place at 3, 7, and 9 months, following randomization and initiation of the treatment process. If participant shows clinical and mycological clearance prior to 9 months follow up, the participant may discontinue application of the topical nail solution if desired, in keeping with general clinical practice. The primary efficacy endpoint will occur at the minimum duration of 7-9 months, in keeping with the aforementioned and subsequently reviewed, proposed study timeline.

Timeline

The general design of this study is that of a randomized, controlled trial, wherein the intervention arms of the study consist of the application of either placebo or active topical nail solution, to be performed on volunteer human participants. The proposed study timeline is denoted in Table 2 and Fig. 1, below.

Milestone	Months
Screening visit and enrollment	12
3-month follow up visit	15
7-month follow up visit	18
9-mont follow up visit	21
Data analysis	27
Submit for publication	30

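### The clinical-cure rule (a fall of at least 60% in VNPIS) cannot be met by a nail scoring 17 or less at baseline, because the stated scale stops at 7

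*Protocol*

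**What the plan says.** The protocol section on the VNPIS describes the scale this way: "The score ranges from a low of 7 to a maximum of 27, with a lower score indicative of a more normal appearing toenail". The total row of Table 3 repeats the range: "TOTAL SCORE (range 7 to 27)". The same section sets the threshold: a decrease of 60% or more "at any follow up visit will be considered a clinical cure".

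Table 3 adds four items. Three are select-one: type (1 to 4 points), longitudinal extent (2 to 4) and percentage involvement (2 to 5). The fourth, gross appearance, is select-all, with features worth 2, 3, 4 and 5. No item has a level for a normal nail.

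Inclusion criterion 4 admits nails with 10% to 100% involvement and any thickness. It sets no minimum VNPIS.

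On timing, the section Duration of Administration says: "Follow-up inspections will take place at 3, 7, and 9 months". Study Duration says: "The 9-month follow up visit will serve as the primary efficacy endpoint". The Study Summary and both of those sections allow application to end before 9 months when the nail is clinically and mycologically cured or clear.

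Statistical Methods names absence of hyphae on PAS stain as the primary endpoint. It names change in VNPIS as a secondary endpoint.

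**The concern.** A percentage fall is a fair yardstick only if the scale can reach zero or the floor is allowed for. Here the best stated score is 7, so the largest possible percentage fall depends on where the nail started. Below some baseline the threshold is out of reach even for a nail that ends with the best score available.

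Clinical-cure status would then be partly fixed at enrolment. Mildly and moderately affected nails would be non-cures by construction in both arms. A reported clinical cure rate would reflect the baseline mix as well as treatment, and would be pulled down in both arms.

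The rule also orders nails oddly. A nail that improves from 25 to 10 qualifies, while a nail that starts at 10 and reaches 7 does not.

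**Working it through.** **Inputs.** Item points come from Table 3, and the range and the 60% threshold from the VNPIS section. The onychauxis feature is taken as 4 points, the value needed to reach the stated maximum.

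**1. Reproduce the stated range.**
- Minimum, with one appearance feature ticked: 1 + 2 + 2 + 2 = 7.
- Maximum, with all features ticked: 4 + 4 + 5 + (2 + 3 + 4 + 5) = 27.

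Both ends agree with the protocol, which shows that the stated minimum assumes at least one appearance feature.

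**2. Baseline needed.** For baseline B and floor F, the largest possible fall is (B − F)/B. Requiring (B − F)/B ≥ 0.60 gives B ≥ F/0.4. With F = 7, B ≥ 17.5, so the lowest whole score is 18.

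| Baseline | Largest possible fall (to 7) | Can qualify? |
|---|---|---|
| 8 | 12.5% | no |
| 10 | 30.0% | no |
| 14 | 50.0% | no |
| 16 | 56.2% | no |
| 17 | 58.8% | no |
| 18 | 61.1% | yes, only at exactly 7 |
| 20 | 65.0% | yes, at 7 or 8 |
| 27 | 74.1% | yes, at 10 or below |

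**3. What a score below 18 looks like.** A distal subungual nail that extends proximal to the lunula, is more than 75% involved, and is thickened and lifted scores 2 + 4 + 5 + 2 + 3 = 16. It cannot qualify.

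**4. Count of profiles.** With type fixed at distal subungual (2 points) and at least one appearance feature, there are 3 × 4 × 15 = 180 combinations, scoring 8 to 25.
- 119 of 180 (66%) score below 18.
- All 48 profiles with a single appearance feature are among them; their maximum is 16.

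**5. Sensitivity to how an improved nail is scored.** Baselines are the same 180 profiles.

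| Assumption at follow-up | Floor | Lowest baseline that can qualify | Profiles that cannot qualify |
|---|---|---|---|
| As stated | 7 | 18 | 119/180 |
| Nail still typed distal subungual, one feature ticked | 8 | 20 | 148/180 |
| No appearance box ticked | 5 | 13 | 33/180 |
| No appearance box ticked, still typed distal subungual | 6 | 15 | 66/180 |

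The last two rows contradict the minimum of 7 that the protocol states twice.

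**The case against.** **Scoring of a cleared nail.** The strongest reply is that the protocol does not say how a cleared nail is scored. The appearance item is select-all, so ticking nothing is a natural reading. The cut-off then drops to 13, and 33 of 180 profiles are excluded rather than 119. If raters leave every item blank, there is no barrier at all. This stands as a limit on the size of the problem, but not as a rescue. Each such reading makes the stated minimum wrong, so the scale and the threshold remain inconsistent.

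**Patient numbers.** A reader might infer that about two thirds of participants cannot be clinically cured. The documents do not support that. The 66% weights every score combination equally, no baseline distribution is given, and the index nail is by rule the most involved one.

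**Main analyses.** A reader might also infer that the main efficacy comparison fails. It does not. The primary endpoint is PAS mycology, and the secondary endpoint is change in score, which can be analysed despite the floor. No passage names a clinical cure rate as an endpoint or gives it a test. The sample-size section speaks only of cured or not cured, but Statistical Methods identifies the primary endpoint as the PAS result.

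**Any-visit clause.** It is tempting to call this clause an error to be replaced by month 9 alone. The clause does let a fall at month 3 count even if it is lost by month 9, and no persistence is required. But application may end early, and PAS is repeated at termination, at 3, 7 or 9 months. A cure that can be assessed at each visit fits that design, so what the documents support is a call for consistency.

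**Conclusion.** The definition is wrong as written, and the severity is moderate. On the protocol's own range, no baseline from 7 to 17 can satisfy the clinical-cure rule, although such nails are eligible. The result rests on two plain readings: the 60% is taken on the raw score, and the minimum is 7 as stated. If the fall were meant on the score above its minimum the barrier would disappear, but the protocol does not say so.

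The damage is confined to the clinical-cure classification: any cure rate reported from it, and the clinical part of the early-stopping condition if that relies on this definition. The primary PAS comparison and the analysis of change in VNPIS are not invalidated. How many participants are affected cannot be determined from the protocol.

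**What to change.** Make the scale and the threshold consistent in one of two ways.

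1. **Give a clear nail a score.** Add a level of none / clear nail = 0 to each of the four Table 3 items and restate the range as 0 to 27. Every nail can then reach a 60% fall. The cost is an edit to Table 3 and the case report forms, plus rescoring of nails already rated, from photographs where these are adequate. The inter- and intra-rater correlations quoted in the protocol refer to the old scale, and this should be stated.

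2. **Keep the scale and allow for its floor.** Define the percentage fall on VNPIS minus 7. This takes one sentence and no rescoring, but it has two consequences to state:
   - It relaxes the rule for severe nails. From 25, the score above the minimum is 18, and 0.4 × 18 = 7.2, so a follow-up score of 14 would qualify, against 10 now.
   - A nail that stays typed distal subungual has a floor of 8. (B − 8)/(B − 7) ≥ 0.60 gives B ≥ 9.5, so baselines of 8 and 9 would still be unable to qualify without a change of type.

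The first option is cleaner because it also gives a normal nail a valid score. It does not change the fact that a fall from 25 to 10 counts as a cure.

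Separately, reconcile the any-visit wording in the VNPIS section, the 9-month efficacy endpoint in Study Duration, and the early-stopping passages in the Study Summary, Study Duration and Duration of Administration. No stopping or clinical rule is proposed here.
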